Cohort	Participant ID	Visit ^a	Rod1 Intercept Time (minutes)	Change from Baseline
1	NEI001	Baseline	X.X	
		Treatment Completion	X.X	
	NEI002	Post-treatment Follow-up	X.X	X.X
		Baseline	X.X	X.X
...	NEI001	Treatment Completion	X.X	X.X
		Post-treatment Follow-up	X.X	X.X
	NEI002	...		
		...		

^a Treatment completion visit corresponds to Month 2 in Cohort 1, and Month 1 in Cohort 2. Post-treatment follow-up visit corresponds to Month 3 in Cohort 1, and Month 2 in Cohort 2.

Listing 2. LLVA Total Letters Read in Study Eye from Baseline to Treatment Completion and Post-Treatment Follow-Up

Cohort	Participant ID	Visit ^a	LLVA Total Letters Read	Change from Baseline
1	NEI001	Baseline	X	
		Treatment Completion	X	X
	NEI002	Post-treatment Follow-up	X	X
		Baseline	X	X
...	NEI001	Treatment Completion	X	X
		Post-treatment Follow-up	X	X
	NEI002	...		
		...		

^a Treatment completion visit corresponds to Month 2 in Cohort 1, and Month 1 in Cohort 2. Post-treatment follow-up visit corresponds to Month 3 in Cohort 1, and Month 2 in Cohort 2.

Listing 3. LLQ Subscale and Composite Scores from Baseline to Treatment Completion and Post-Treatment Follow-Up

Cohort	Participant ID	Visit ^b	Driving			Extreme Lighting			Mobility			Emotional Distress			General dim Lighting			Peripheral Vision			Composite Score ^a		
			Score	Δ^c	Score	Δ^c	Score	Δ^c	Score	Δ^c	Score	Δ^c	Score	Δ^c	Score	Δ^c	Score	Δ^c	Score	Δ^c	Score	Δ^c	
1	NEI001	Baseline	xx		xx		xx		xx		xx		xx		xx		xx		xx		xx		xx
		Treatment Completion	xx		xx		xx		xx		xx		xx		xx		xx		xx		xx		xx
		Post-treatment Follow-up	xx		xx		xx		xx		xx		xx		xx		xx		xx		xx		xx
2	NEI002	Baseline	xx		xx		xx		xx		xx		xx		xx		xx		xx		xx		xx
		Treatment Completion	xx		xx		xx		xx		xx		xx		xx		xx		xx		xx		xx
		Post-treatment Follow-up	xx		xx		xx		xx		xx		xx		xx		xx		xx		xx		xx
...																							

^aScore and Δ rounded to the nearest tenth.^aComposite score is an average of the six weighted subscale scores.^bTreatment completion visit corresponds to Month 2 in Cohort 1, and Month 1 in Cohort 2. Post treatment follow-up visit corresponds to Month 3 in Cohort 1, and Month 2 in Cohort 2.^c Δ implies change from baseline.

Figure 1. Study Disposition

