3.3 Study Population

Five participants with AMD who met the eligibility criteria were enrolled into Cohort 1. Enrollment for Cohort 1 was halted on May 24, 2019 to focus on enrollment for Cohort 2. Up to five participants with AMD who meet the eligibility criteria may be enrolled in Cohort 2. Up to five additional participants may be accrued in the Cohort 2 to account for participants who withdraw from the study prior to receiving one month of study supplementation for a reason unrelated to an adverse reaction. Participants in Cohort 1 may enroll into Cohort 2 as long as their last intake of vitamin A palmitate was greater than two months prior to their enrollment into Cohort 2.

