11.0 EXPLORATORY ANALYSES

11.1 Dark Adaptation Times

To explore the effect of within-subject correlation, a mixed effects model (Model 1) will be fit using PROC MIXED in SAS to assess mean change from baseline in RIT in the study eye at the treatment completion visit and post-treatment follow-up visit in Cohort 1.

$$\text{Model 1: } \hat{Y}_{ij} = \beta_0 + \beta_1 * \text{Time}_j + b_i + \varepsilon_t$$

Where:

\hat{Y}_{ij} = Estimate of mean RIT for participant i at timepoint j

β_0 = Estimate of mean RIT at baseline

β_1 = Estimate of mean rate of change (monthly) in RIT

Time_j = Time in months from baseline

b_i = Random effect for baseline RIT in the i^{th} participant

ε_t = Random variability not explained by the model, which is assumed to be normally distributed and independent across participants and time

Based on this model, the estimated mean difference in RIT between baseline and Month 2 is $2\beta_1$, and the estimated mean difference between baseline and Month 3 is $3\beta_1$. The following hypothesis will be tested at a type I error rate of 5%:

$$H_0: \beta_1 = 0$$

$$H_A: \beta_1 \neq 0$$

The results of this analysis will be summarized as in Table 9.

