Cells highlighted in green correspond to the primary outcome analysis; cells highlighted in yellow correspond to secondary analyses and the remaining analyses correspond to exploratory analyses.

^a Paired t-test comparing RIT at treatment completion visit or post-treatment follow-up visit vs. baseline at two-sided type 1 error rate of 5%.

^b Mixed-effects longitudinal model conducted at two-sided type 1 error rate of 5%. The coefficient β_1 corresponds to the estimate of the mean rate of change(monthly) in DA RIT. [COV] covariance structure provided the best model fit.

^c Treatment completion visit corresponds to Month 2 in Cohort 1, and Month 1 in Cohort 2. Post-treatment follow-up visit corresponds to Month 3 in Cohort 1, and Month 2 in Cohort 2.

^d Δ implies change from baseline.

Programming note: Replace [COV] with actual covariance structure that provided the best model fit.

Table 10. Analysis of Secondary Outcome of Change in LLVA Total Letters Read from Baseline in the Study Eye and Corresponding Exploratory Analyses

Visit ^c	Cohort 1						Cohort 2					
	Total Letters Read			Paired T-Test ^a			Mixed-Effects Model ^b			Total Letters Read		
	Mean	(95% CI)	p-value	β_1	SE (β_1)	p-value	Value	Value	Δ^d	Mean	(95% CI)	p-value
Baseline												
N	x									x		
Mean (SD)	x.x (x.xx)									x.x (x.xx)		
Median	x.x									x.x		
Range (min, max)	(x, x)									(x, x)		
Treatment Completion												
N	x									x		
Mean (SD)	x.x (x.xx)			x.x (x.xx)						x.x (x.xx)		
Median	x.x			x.x						x.x		
Range (min, max)	(x, x)			(x, x)						(x, x)		
Statistical Test												
	x.xx			x.xxx			x.xxx		x.xxx	x.xxx		
											x.xxx	
												x.xxx
Post-treatment Follow-up												
N	x									x		
Mean (SD)	x.x (x.xx)			x.x (x.xx)						x.x (x.xx)		
Median	x.x			x.x						x.x		
Range (min, max)	(x, x)			(x, x)						(x, x)		
Statistical Test												
	x.x			x.xxx			x.xxx		x.xxx	x.xxx		
											x.xxx	
												x.xxx

Cells highlighted in yellow correspond to the secondary outcome analysis, and the remaining analyses correspond to exploratory analyses

^aPaired t-test comparing LLVA at treatment completion visit or post-treatment follow-up visit vs. baseline at two-sided type 1 error rate of 5%.

^bMixed-effects longitudinal model conducted at two-sided type 1 error rate of 5%. The coefficient β_1 corresponds to the estimate of the mean rate of change (monthly) in LLVA total letters read. [COV] covariance structure provided the best model fit.

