^b Mixed-effects longitudinal model conducted at two-sided type I error rate of 5%. The coefficient β_1 corresponds to the estimate of the mean rate of change (monthly) in the score. The mixed-effects model was fit for the composite score only. [COV] covariance structure provided the best model fit.

^c Treatment completion visit corresponds to Month 2 in Cohort 1, and Month 1 in Cohort 2. Post-treatment follow-up visit corresponds to Month 3 in Cohort 1, and Month 2 in Cohort 2.

^d Δ implies change from baseline.

^e Composite score is an average of the six weighted subscale scores.

Programming note: Replace [COV] with actual covariance structure that provided the best model fit.

Table 12. Summary of Adverse Events (AEs)

	Participants with Events			Number of Events		
	N (%) ^a			N		
	Cohort 1 (N=X)	Cohort 2 (N=X)	Overall (N=X)	Cohort 1	Cohort 2	Overall
All AEs	x (x)	x (x)	x (x)	x	x	x
Serious Adverse Events	x (x)	x (x)	x (x)	x	x	x
Severity						
Mild	x (x)	x (x)	x (x)	x	x	x
Moderate	x (x)	x (x)	x (x)	x	x	x
Severe	x (x)	x (x)	x (x)	x	x	x
Life-threatening	x (x)	x (x)	x (x)	x	x	x
Death	x (x)	x (x)	x (x)	x	x	x
Ocular Specification						
Non-ocular	x (x)	x (x)	x (x)	x	x	x
Study Eye	x (x)	x (x)	x (x)	x	x	x
Fellow Eye	x (x)	x (x)	x (x)	x	x	x
Outcome						
Resolved	x (x)	x (x)	x (x)	x	x	x
Resolved with sequelae	x (x)	x (x)	x (x)	x	x	x
Death	x (x)	x (x)	x (x)	x	x	x
Resolved by convention	x (x)	x (x)	x (x)	x	x	x
Relation to IP						
Related	x (x)	x (x)	x (x)	x	x	x
Not Related	x (x)	x (x)	x (x)	x	x	x

^aColumn header counts and denominators are the number of participants in the safety population in the respective cohort or overall. Participants may be counted in more than one category. Percentages are rounded to the nearest whole number.

Table 13. AEs by System Organ Class (SOC) and Preferred Term (PT)

MedDRA System Organ Class/ Preferred Term ^{a,b}	Participants with Events			Number of Events		
	N (%) ^c			N		
	Cohort 1 (N=X)	Cohort 2 (N=X)	Overall (N=X)	Cohort 1	Cohort 2	Overall
SOC1	x (x)	x (x)	x (x)	x	x	x
PT1	x (x)	x (x)	x (x)	x	x	x
PT2	x (x)	x (x)	x (x)	x	x	x
...	x (x)	x (x)	x (x)	x	x	x
SOC2	x (x)	x (x)	x (x)	x	x	x
PT1	x (x)	x (x)	x (x)	x	x	x
PT2	x (x)	x (x)	x (x)	x	x	x
...	x (x)	x (x)	x (x)	x	x	x
...	x (x)	x (x)	x (x)	x	x	x

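### SAP 11.1 fixes the covariance of Model 1, but Tables 9 to 11 let the data of five participants choose it, so the stated 5% level of the slope test is not assured

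*SAP*

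**What the plan says.** SAP 11.1 defines Model 1 for RIT in Cohort 1, to be fitted with PROC MIXED. It has a fixed intercept, a linear time slope β1 and one random term per participant, described as "Random effect for baseline RIT in the" i-th participant. The error term is "Random variability not explained by the model, which is assumed to be normally distributed and independent across participants and time". The test of β1 is introduced by "The following hypothesis will be tested at a type I error rate of 5" percent, with a two-sided alternative. The section names no other covariance structure and no selection step. SAP 11.2 and 11.3 apply a similar model to low luminance visual acuity (LLVA) and to the composite score of the low luminance questionnaire (LLQ).

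The table shells in SAP 18.0 describe something else. Footnote b of Table 9 begins "Mixed-effects longitudinal model conducted at two-sided type 1 error rate of 5" percent and ends by saying that the structure to be filled in "covariance structure provided the best model fit". A note to the programmer follows: "Programming note: Replace [COV] with actual covariance structure that provided the best model fit". Table 10 repeats both. Footnote b of Table 11 reads "The mixed-effects model was fit for the composite score only. [COV] covariance structure provided the best model fit", again with the programming note.

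On numbers, SAP 3.3 says "Five participants with AMD who met the eligibility criteria were enrolled into Cohort 1". SAP 5.6 and the opening of SAP 5.0 label all analyses exploratory.

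**The concern.** A random intercept with independent residuals is a complete covariance specification: equal variances and equal correlations between visits (compound symmetry). A rule that puts the best-fitting structure in its place is a different analysis, and a programmer cannot carry out both.

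The choice also affects the error rate. With five people, a flexible structure can fit best by chance. Its parameters are then treated as known when the standard error of the slope is computed, so that standard error tends to be too small. At stake is the p-value for β1 in Tables 9 to 11, which the footnotes label as a 5% test. In Table 9 it is printed beside the primary result.

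**Working it through.** **Inputs from the documents.** N = 5 (SAP 3.3). Two-sided 5% (SAP 11.1; Table 9, footnote b). SAP 11.1 and the Table 9 shell name baseline, treatment completion and post-treatment follow-up, which in Cohort 1 are months 0, 2 and 3. Month 1 RIT is also collected (SAP 14.1, Table 15), so a four-visit fit is possible although it is not named.

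**Assumptions, because the documents give no figures.** Between-person SD 5 minutes and residual SD 3 minutes. Candidates are independence (VC), compound symmetry (CS), AR(1) and unstructured (UN). The criterion is AIC, BIC, AICC or −2 log-likelihood. Fits are by REML.

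**Step 1: the plan's own figure.** Under Model 1 with complete data, the slope test is a t-test on N×T − N − 1 degrees of freedom: 15 − 5 − 1 = 9 with three visits and 20 − 5 − 1 = 14 with four. It is exact in theory. Simulation with slope zero and 1,000 datasets gives 4.7% and 4.8%. The Monte Carlo standard error at 5% is √(0.05×0.95/1000) = 0.7 points. The stated 5% is reproduced.

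**Step 2: what a flexible structure asks of the data.** UN has T(T+1)/2 parameters: 3×4/2 = 6 with three visits and 4×5/2 = 10 with four, all from five people. Model 1 has 2.

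**Step 3: type I error when the structure is chosen first, with Model 1 true.** Ranges in the AIC, BIC and −2 log-likelihood rows run over testing UN on N − 1 = 4 df or on between-within df.

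| Rule | Months 0, 2, 3 | Months 0, 1, 2, 3 |
|---|---|---|
| Model 1 as written, no choice | 4.7% | 4.8% |
| AIC, UN a candidate | 10.2–11.5% | 19.8–22.6% |
| AIC, UN a candidate, Kenward-Roger df | 8.6% | 15.3% |
| BIC, UN a candidate | 12.0–14.0% | 24.3–28.5% |
| −2 log-likelihood (always takes UN) | 13.5–18.7% | 30–38% |

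With AICC the error is 4.3–6.0%. With neither UN nor heterogeneous-variance structures among the candidates it is about 4–5%.

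Separately coded repeats of the AIC scenario with CS, AR(1) and UN gave 8.5–10.8% on three visits and 18.5–20.0% on four. Fixed CS gave 4.7–5.3% and 5.0–5.2%. In one of these repeats UN was chosen in 29% and 44% of datasets although CS was true.

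**Step 4: if Model 1 is not true.** With AR(1) correlation of 0.7, or a random slope with SD 1, and three visits, fixed Model 1 rejects in about 7% of datasets. AIC selection with UN as a candidate rejects in 8.5–12.6%.

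**The case against.** The strongest reply is that little depends on this model. It stands under the exploratory analyses, covers Cohort 1 only, and comes from a plan that makes no multiplicity adjustment. The covariance wording also looks deliberate: the SAP version history records adding it to these three tables, and SAP 11.1 gives the model's aim as exploring within-subject correlation. All of this stands, and it limits the severity. It does not tell the programmer which text to follow.

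A second reply is that the inflation comes from assumptions. That is largely right. It needs a very flexible structure among the candidates and a criterion without small-sample correction, and the SAP states neither. The comparison in Step 3 also favours Model 1, because the data were generated under it; Step 4 gives the fairer comparison.

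Three stronger readings are tempting, and the documents do not support them:
- A reader might infer that the plan has one particular inflated error rate. It does not, because the candidates and the criterion are not stated. The figures near 20% also need a Month 1 visit that neither SAP 11.1 nor the Table 9 shell names.
- A reader might infer that the primary result is compromised. The primary RIT test is the paired t-test of SAP 9.1, and the visit-by-visit LLVA and LLQ tests are also paired t-tests. None involves a covariance choice.
- A reader might infer that the same inflation would follow if visit replaced linear time. The SAP has no such model, and simulated contrasts of one visit against baseline rejected only about 4–7% after selection.

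**Conclusion.** The contradiction is on the page and recurs in all three tables. If the table rule is followed, the 5% stated for β1 is not assured. The size depends on what the SAP leaves open: about 9–12% for AIC with UN as a candidate on the three named visits, about 19–23% if Month 1 is added, and from about 4% to 30% or more across all the options. These figures rest on five participants with complete data, the assumed SDs of 5 and 3 minutes, and Model 1 being true. Model 1 as written holds about 5% under those conditions and about 7% under the two departures tried. The severity is minor, because the effect is confined to an exploratory model in one cohort.

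**What to change.** Make the SAP 11.1 structure (random intercept, independent residuals, REML) the single prespecified covariance for the mixed-model p-values in Tables 9, 10 and 11. State the degrees-of-freedom method and which visits enter the model. With complete data the slope test is already exact under Model 1, so a Kenward-Roger correction would add little. Delete the best-fit sentence from footnote b and the programming note from all three tables. Any other structure may be shown only as a labelled sensitivity analysis.

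Listing the candidates, the criterion (for example AICC) and the degrees-of-freedom method in SAP 11.1, with Model 1 as the reference result, would also remove the contradiction. It is more work for five participants.

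The cost is SAP wording only, with no new data and slightly less analysis. The downside is that the model is not tuned if the correlation differs between visits.
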